3.3 Inclusion of Women and Minorities

Both men and women and members of all races and ethnic groups are eligible for this trial.

4.0 REGISTRATION PROCEDURES

Patients must not start any protocol intervention prior to registration through the Siteman Cancer Center.

The following steps must be taken before registering patients to this study:

1. Confirmation of patient eligibility

2. Registration of patient in the Siteman Cancer Center Oncore database
3. Assignment of unique patient number (UPN)

4.1 Confirmation of Patient Eligibility

Confirm patient eligibility by collecting the information listed below:

1. Registering MD's name
2. Patient's race, sex, and DOB
3. Three letters (or two letters and a dash) for the patient's initials
4. Copy of signed consent form
5. Completed eligibility checklist, signed and dated by a member of the study team
6. Copy of appropriate source documentation confirming patient eligibility

4.2 Patient Registration in the Siteman Cancer Center Oncore Database

All patients must be registered through the Siteman Cancer Center.

4.3 Assignment of UPN

Each patient will be identified with a unique patient number (UPN) for this study. All data will be recorded with this identification number on the appropriate CRFs.

5.0 TREATMENT PLAN

This is an open label, single-arm phase II trial focusing on the response rate of everolimus. The study treatment plan is as follows:

1. Everolimus 10 mg orally, once daily
2. Follow-up CT scan 8 weeks later and then every two months for disease assessment
3. Discontinue everolimus at the time of progression as defined by RECIST 1.1 criteria
4. Follow up biopsy (of accessible lesions that clearly showed progression)

5.1 Agent Administration

Everolimus is an oral drug which will be administered on an outpatient basis at a dose of 10 mg daily on a 28-day cycle. Patients should take everolimus at approximately the same time every day, either consistently with or consistently without food. The tablets should be swallowed whole with a glass of water and should not be chewed or crushed. The glass should be rinsed with the same volume of water and the rinse completely swallowed to ensure the entire dose is administered. If vomiting occurs, no attempt should be made to replace the vomited dose. If a patient misses a dose, the patient should be instructed not to take or make up that dose and to resume dosing with the next scheduled dose. Patients will be instructed to bring all unused tablets and their medication diary (see Appendix B) to each study visit for assessment of compliance.

5.2 Supportive Care Guidelines

Overall, safety data available from completed, controlled and uncontrolled studies indicate that everolimus is generally well tolerated at weekly or daily dose schedules. The safety profile is characterized by manageable adverse events (AEs). These AEs are generally reversible and non-cumulative.

Adverse events most frequently observed with everolimus are stomatitis, rash, diarrhea, fatigue, infections, asthenia, nausea, peripheral edema, decreased appetite, headache, dysgeusia, epistaxis, mucosal inflammation, pneumonitis, weight decreased, vomiting, pruritus, cough, dyspnea, dry skin, nail disorder, and pyrexia. Overall, the most frequently observed laboratory abnormalities include decreased hematology parameters including hemoglobin, lymphocytes, platelets, and neutrophils (or collectively as pancytopenia); increased clinical chemistry parameters including cholesterol, triglycerides, glucose, aspartate transaminases, creatinine, alanine transaminases, and bilirubin; and decreased clinical chemistry parameters including phosphate and potassium. The majority of these AEs have been of mild to moderate severity (NCI CTC grade 1-2).

5.2.1 Management of infections

Everolimus has immunosuppressive properties and may predispose patients to bacterial, fungal, viral or protozoal infections, including infections with opportunistic pathogens. Localized and systemic infections, including pneumonia, other bacterial infections, invasive fungal infections, such as aspergillosis or candidiasis and viral infections including reactivation of hepatitis B virus, have been described in patients taking everolimus. Some of these infections have been severe (e.g. leading to sepsis, respiratory or hepatic failure) and occasionally have had a fatal outcome.

Physicians and patients should be aware of the increased risk of infection with everolimus. Treat pre-existing infections prior to starting treatment with everolimus. While taking everolimus, be vigilant for symptoms and signs of infection; if a diagnosis of infection is made, institute appropriate treatment promptly and consider interruption or discontinuation of everolimus.

If a diagnosis of invasive systemic fungal infection is made, discontinue everolimus and treat with appropriate antifungal therapy.

Cases of pneumocystis jirovecii pneumonia (PJP), some with a fatal outcome, have been reported in patients who received everolimus. PJP may be associated with concomitant use of corticosteroids or other immunosuppressive agents. Prophylaxis for PJP should be considered when concomitant use of corticosteroids or other immunosuppressive agents are required.

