5.2.6 Management of stomatitis / oral mucositis / mouth ulcers

Severity	Everolimus Dose Adjustment and Management Recommendations
Grade 1 (Minimal symptoms, normal diet)	No dose adjustment required. Manage with non-alcoholic or salt water (0.9%) mouth wash several times a day.
Grade 2 (Symptomatic but can eat and swallow modified diet)	Temporary dose interruption until recovery to grade ≤ 1 . Re-initiate everolimus at the same dose. If stomatitis recurs at grade 2, interrupt dose until recovery to grade ≤ 1 . Re-initiate everolimus at a lower dose. Manage with topical analgesic mouth treatments (e.g. benzocaine, butyl aminobenzoate, tetracaine hydrochloride, menthol or phenol) with or without topical corticosteroids (i.e. triamcinolone oral paste)*.
Grade 3 (Symptomatic and unable to adequately eat or hydrate orally)	Temporary dose interruption until recovery to grade ≤ 1 . Re-initiate everolimus at lower dose. Manage with topical analgesic mouth treatments (i.e. benzocaine, butyl aminobenzoate, tetracaine hydrochloride, menthol or phenol) with or without topical corticosteroids (i.e. triamcinolone oral paste)*
Grade 4 (Symptoms associated with life-threatening consequences)	Discontinue everolimus and treat with appropriate medical therapy.

* using agents containing alcohol, hydrogen peroxide, iodine, and thyme derivatives in management of stomatitis as they may worsen mouth ulcers.

Patients with a clinical history of stomatitis/mucositis/mouth ulcers and those with gastrointestinal morbidity associated with mouth/dental infections, irritation of esophageal mucosa e.g. gastroesophageal reflux disease (GERD) and pre-existing stomatitis/mucositis must be monitored even more closely. Patients should be instructed to report the first onset of buccal mucosa irritation/reddening to their study physician immediately.

Stomatitis/oral mucositis/mouth ulcers due to everolimus should be treated using local supportive care. Please note that investigators in earlier trials have described the oral toxicities associated with everolimus as mouth ulcers, rather than mucositis or stomatitis. If your examination reveals mouth ulcers rather than a more general inflammation of the mouth, please classify the adverse event as such. The suggested paradigm for treatment of stomatitis/oral mucositis/mouth ulcers is as follows:

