AST or ALT elevation Grade 4 (> 20 x ULN)*	Interrupt everolimus administration until resolution to \leq grade 1 (or \leq grade 2 if baseline values were within the range of grade 2). If resolution occurs \leq 7 days, everolimus should be re-started at one dose level lower. If resolution takes > 7 days, discontinue everolimus.
Recurrence of grade 4 AST or ALT elevation after dose reduction or toxicity requiring everolimus interruption for > 28 days	Discontinue everolimus.
Intolerable grade 2 mucositis, or grade 3 AE, except hyperglycemia or hypertriglyceridemia or hypercholesterolemia (see Section 5.2.8)	Interrupt everolimus administration until resolution to \leq grade 1 or baseline grade / value. If resolution occurs within \leq 7 days, everolimus should be re-started at the dose level prior to interruption. If resolution takes > 7 days, or if event recurs within 28 days, hold everolimus until recovery to \leq grade 1 or baseline grade / value and reintroduce everolimus at one dose level lower, if available. Patients will be withdrawn from the study if they fail to recover to \leq grade 1 or baseline grade / value within 28 days.
Any other grade 4	Hold everolimus until recovery to grade \leq 1 or baseline value Reintroduce everolimus at one dose level lower, if available.
Grade 3 or 4 clinical liver failure (asterixis or encephalopathy/coma)	Discontinue everolimus
Recurrence of intolerable grade 2 mucositis or grade 3 event after dose reduction	Reduce dose to the next lower dose level, if available. The lowest possible dose level of everolimus is 2.5 mg daily. Below this level, everolimus must be discontinued. If toxicity recurs at Grade 3, consider discontinuation
Recurrence of grade 4 after dose reduction	Discontinue everolimus
Any non-hematologic toxicity requiring everolimus interruption for > 28 days	Discontinue everolimus

* Should HCV flare be confirmed, the guidelines for flare must take precedence

Dosing guidelines for Everolimus-related hematologic toxicities

Toxicity	Action
Grade 3 thrombocytopenia, neutropenia, or anemia	Interrupt everolimus until resolution to grade ≤ 1 If resolution occurs ≤ 7 days, reintroduce everolimus at the dose level prior to interruption. If resolution occurs > 7 days, or event occurs within 28 days, reintroduce everolimus at one dose level lower, if available.

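### Section 5.2.6 discontinues everolimus for grade 4 stomatitis, but Section 6's general grade 4 row restarts it one dose level lower; the two sections also give different restart doses for grade 3 stomatitis

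*Combined protocol and SAP*

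**What the plan says.** **Stomatitis.** The table in Section 5.2.6 interrupts everolimus for grade 3 and restarts it at a lower dose. For grade 4, which it describes as life-threatening, it says "Discontinue everolimus and treat with appropriate medical therapy".

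**Metabolic events.** Section 5.2.8 gives the same grade 4 instruction for hyperlipidemia and hyperglycemia.

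**Fungal infection.** Section 5.2.1: "If a diagnosis of invasive systemic fungal infection is made, discontinue everolimus and treat with appropriate antifungal therapy".

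**Section 6, everolimus-related non-hematologic toxicities.**
- There are dedicated rows for pneumonitis (referring to 5.2.9), HBV reactivation or HCV flare (referring to 5.2.10), AST/ALT elevation and clinical liver failure.
- A general row covers "Intolerable grade 2 mucositis, or grade 3 AE, except hyperglycemia or hypertriglyceridemia or hypercholesterolemia (see Section 5.2.8"). If the event resolves within 7 days, "everolimus should be re-started at the dose level prior to interruption"; if it takes longer or recurs within 28 days, the restart is one level lower. The same row adds a limit: "Patients will be withdrawn from the study if they fail to recover" within 28 days.
- A catch-all row for any other grade 4 event holds the drug until recovery and then says to "reintroduce everolimus at one dose level lower, if available". It has no exceptions.
- Two further rows discontinue the drug: "Recurrence of grade 4 after dose reduction" and "Any non-hematologic toxicity requiring everolimus interruption for > 28 days".

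**Suspected pregnancy.** Section 5.4 stops everolimus on suspicion and lets dosing resume once pregnancy is excluded. Section 5.5 lists suspected pregnancy among the criteria that end treatment.

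**The concern.** Both sections give dosing instructions, and for the same grade 4 event one stops the drug while the other restarts it. Where Section 6 means to defer to Section 5 it says so, for pneumonitis, for viral hepatitis and, in the grade 3 row, for metabolic events. It makes no such reference for stomatitis, and it handles grade 2 and 3 mucositis with its own rules. A site dosing from the Section 6 table could therefore re-expose a patient after a life-threatening event for which Section 5 says to stop. The stake is patient safety and uniform handling across patients.

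**Working it through.** The plan gives no figure on this point to reproduce. The check is a rule-by-rule comparison, using the Section 6 dose levels of 10, 5 and 2.5 mg daily. *Discontinue* is taken as 0 mg from then on, and the event is taken to be everolimus-related, because the Section 6 table covers only that.

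| Event, patient on 10 mg | Section 5 | Section 6 | Dose after recovery: Section 5 vs Section 6 |
|---|---|---|---|
| Grade 4 stomatitis, recovery within 28 days | discontinue (5.2.6) | catch-all grade 4 row: hold, one level lower | 0 vs 5 mg |
| Grade 3 stomatitis, resolved within 7 days | restart lower (5.2.6) | grade 3 row: prior dose | 5 vs 10 mg |
| Grade 3 stomatitis, resolved in 8 to 28 days | restart lower (5.2.6) | grade 3 row: one level lower | 5 vs 5 mg, no conflict |
| Grade 4 hyperlipidemia or hyperglycemia, recovery within 28 days | discontinue (5.2.8) | catch-all row, unless *other* excludes it | 0 vs 5 mg, or no conflict |
| Grade 3 invasive fungal infection | discontinue (5.2.1) | grade 3 row, by inference | 0 vs 10 mg (within 7 days) or 5 mg (8 to 28 days) |
| Grade 4 invasive fungal infection, recovery within 28 days | discontinue (5.2.1) | catch-all row, by inference | 0 vs 5 mg |

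**Limits on the grade 4 conflict.** From 5 mg the difference is 0 vs 2.5 mg. From 2.5 mg there is none, because Section 6 requires discontinuation when a further reduction is needed. There is also none when the interruption exceeds 28 days or when the event is a recurrent grade 4 after dose reduction; Section 6 then discontinues too.

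**Limits on the grade 3 stomatitis conflict.** It disappears if the event recurs within 28 days, or recurs after a dose reduction, since Section 6 then also goes down a level.

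**Strength of each item.**
1. Grade 4 stomatitis is the clearest. No Section 6 row names it and no reference sends the reader to 5.2.6.
2. Grade 3 stomatitis is a direct conflict, because it meets the grade 3 row and that row exempts only the metabolic events.
3. Grade 4 metabolic events are ambiguous. The reference to 5.2.8 is in the grade 3 row and is not repeated for grade 4.
4. Fungal infection is inferred. Section 6 does not mention it, so a case reaches the general rows only through its grade.
5. Pregnancy is minor. Both sections stop the drug on suspicion; they differ on whether a patient found not to be pregnant may return.

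**Precedence.** The only precedence rule in the Section 6 tables concerns HCV flare. Nothing ranks 5.2.1, 5.2.6 or 5.2.8 against the general rows.

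**The case against.** The best defence is that a specific instruction outranks a general one, and that Section 6 does not stand alone. It refers back to 5.2.8, 5.2.9 and 5.2.10. It calls its content recommendations, leaves management to the treating physician's judgment, and has a sentence about *proceeding* sections that may be meant to point back to Section 5. Section 5.5 also ends treatment for adverse events that the investigator judges may cause severe or permanent harm, whichever table is in use. Finally, *discontinue* is nowhere defined as permanent, and 5.4 uses it for a stop that can be reversed.

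Much of this stands for the weaker items. *Other* in the catch-all row can fairly be read as leaving metabolic events to 5.2.8. The fungal rule is triggered by a diagnosis, and most physicians would follow it. Section 5.3.1 also advises against strong CYP3A4 inhibitors such as itraconazole, which discourages a restart during some antifungal courses.

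It does not remove the stomatitis conflict. Section 6 gives its own mucositis rules, so the topic is not left to Section 5. The judgment sentence and the 5.5 criterion soften both instructions without saying which is the default. On the meaning of *discontinue*, 5.2.1 offers interruption and discontinuation as alternatives, and the tables in 5.2.6 and 5.2.8 use temporary interruption below grade 4, so a lasting stop is the more natural reading. If it meant only a hold, the grade 4 difference would shrink to 5.2.6 being silent on restart; the grade 3 conflict would remain.

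A reader might infer that Section 6 obliges a site to restart the drug after a life-threatening event. The judgment sentence and 5.5 rule that out: Section 6 permits a restart but does not compel one.

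**Conclusion.** The plan is wrong as written: its dosing rules contradict each other for grade 4 stomatitis and for grade 3 stomatitis that resolves within 7 days. The metabolic item is an ambiguity, the fungal item an inferred gap, and the pregnancy item a minor inconsistency.

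For grade 4 stomatitis the size is 0 vs 5 mg from 10 mg, or 0 vs 2.5 mg from 5 mg. For grade 3 it is one dose level. These figures assume that the event is everolimus-related, that recovery falls within the stated limits and, for grade 4, that *discontinue* is lasting. The documents give no frequency for these specific events, so the number affected among the 12 patients cannot be estimated.

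Two stronger readings should be resisted. A reader might infer a fetal-exposure gap from 5.4 and 5.5, but both stop the drug as soon as pregnancy is suspected. A reader might also infer damage to the primary analysis; the rule of 2 or more responders among 12 does not depend on these dosing rules, and no statistical property changes. The case for correction is safety and consistency, at very low cost.

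**What to change.** In a short amendment:
1. Reword the Section 6 catch-all row to *Any other grade 4, except stomatitis (see 5.2.6), hyperlipidemia or hyperglycemia (see 5.2.8) and invasive systemic fungal infection (see 5.2.1)*.
2. Add *except invasive systemic fungal infection (see 5.2.1)* to the grade 3 row.
3. Have the medical team choose one restart dose for grade 3 stomatitis and state it in both 5.2.6 and Section 6.
4. State whether *discontinue* is permanent.
5. Change the 5.5 bullet to *Confirmed pregnancy (hold on suspicion per 5.4)*.

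A blanket sentence that Section 5 governs is not advised until the stomatitis rules are reconciled, because a first grade 2 event differs too: 5.2.6 restarts at the same dose, while Section 6 drops a level if the event is intolerable and takes more than 7 days to resolve.

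The change needs no additional patients or procedures. Its downside is that a patient whose grade 4 stomatitis or metabolic event resolves loses the option of a lower-dose restart, so the medical team should first confirm that Section 5 states the intended rule.

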5.2.2 Management of skin toxicity

For patients with grade 1 toxicity, no specific supportive care is usually needed or indicated. Rash must be reported as an AE. Patients with grade 2 or higher toxicity may be treated with the following suggested supportive measures at the discretion of the investigator: oral minocycline, topical tetracycline, topical clindamycin, topical silver sulfadiazine, diphenhydramine, oral prednisolone (short course), topical corticosteroids, or pimecrolimus.

5.2.3 Management of hypersensitivity reactions

Hypersensitivity reactions manifested by symptoms including, but not limited to, anaphylaxis, dyspnea, flushing, chest pain or angioedema (e.g. swelling of the airways or tongue, with or without respiratory impairment) have been observed with everolimus.

5.2.4 Angioedema with concomitant use of angiotensin-converting enzyme (ACE) inhibitors

Patients taking concomitant ACE inhibitor therapy may be at increased risk for angioedema (e.g. swelling of the airways or tongue, with or without respiratory impairment).

5.2.5 Renal Failure Events

Cases of renal failure (including acute renal failure), some with fatal outcome, occurred in patients treated with everolimus. Renal function of patients should be monitored particularly where patients have additional risk factors that may further impair renal function.

Elevations of serum creatinine, usually mild, and proteinuria have been reported in patients taking everolimus. Monitoring of renal function, including measurement of blood urea nitrogen (BUN), urinary protein, or serum creatinine, is recommended prior to the start of everolimus therapy and periodically thereafter.

5.2.6 Management of stomatitis / oral mucositis / mouth ulcers

Severity	Everolimus Dose Adjustment and Management Recommendations
Grade 1 (Minimal symptoms, normal diet)	No dose adjustment required. Manage with non-alcoholic or salt water (0.9%) mouth wash several times a day.
Grade 2 (Symptomatic but can eat and swallow modified diet)	Temporary dose interruption until recovery to grade ≤ 1 . Re-initiate everolimus at the same dose. If stomatitis recurs at grade 2, interrupt dose until recovery to grade ≤ 1 . Re-initiate everolimus at a lower dose. Manage with topical analgesic mouth treatments (e.g. benzocaine, butyl aminobenzoate, tetracaine hydrochloride, menthol or phenol) with or without topical corticosteroids (i.e. triamcinolone oral paste)*.
Grade 3 (Symptomatic and unable to adequately eat or hydrate orally)	Temporary dose interruption until recovery to grade ≤ 1 . Re-initiate everolimus at lower dose. Manage with topical analgesic mouth treatments (i.e. benzocaine, butyl aminobenzoate, tetracaine hydrochloride, menthol or phenol) with or without topical corticosteroids (i.e. triamcinolone oral paste)*
Grade 4 (Symptoms associated with life-threatening consequences)	Discontinue everolimus and treat with appropriate medical therapy.

* using agents containing alcohol, hydrogen peroxide, iodine, and thyme derivatives in management of stomatitis as they may worsen mouth ulcers.

Patients with a clinical history of stomatitis/mucositis/mouth ulcers and those with gastrointestinal morbidity associated with mouth/dental infections, irritation of esophageal mucosa e.g. gastroesophageal reflux disease (GERD) and pre-existing stomatitis/mucositis must be monitored even more closely. Patients should be instructed to report the first onset of buccal mucosa irritation/reddening to their study physician immediately.

Stomatitis/oral mucositis/mouth ulcers due to everolimus should be treated using local supportive care. Please note that investigators in earlier trials have described the oral toxicities associated with everolimus as mouth ulcers, rather than mucositis or stomatitis. If your examination reveals mouth ulcers rather than a more general inflammation of the mouth, please classify the adverse event as such. The suggested paradigm for treatment of stomatitis/oral mucositis/mouth ulcers is as follows:

1. For mild toxicity (grade 1), no dose adjustment required. Manage with non-alcoholic mouth wash or salt water (0.9%) mouth wash several times a day until resolution.
2. For more severe toxicity (grade 2 in which case patients have pain but are able to maintain adequate oral alimentation, or grade 3 in which case patients cannot maintain adequate oral alimentation), the suggested treatments are topical analgesic mouth treatments (i.e., local anesthetics such as, benzocaine, butyl aminobenzoate, tetracaine hydrochloride,

menthol, or phenol) with or without topical corticosteroids, such as triamcinolone oral paste 0.1% (Kenalog in Orabase[®]).

3. Agents containing alcohol, hydrogen peroxide, iodine, and thyme derivatives may tend to worsen mouth ulcers. These agents should be avoided.
4. Antifungal agents should be avoided unless a fungal infection is diagnosed. In particular, systemic imidazole antifungal agents (ketoconazole, fluconazole, itraconazole, etc.) should be avoided in all patients due to their strong inhibition of everolimus metabolism, therefore leading to higher everolimus exposures. Therefore, topical antifungal agents are preferred if an infection is diagnosed.

